### 3. Asthma APGAR:

The Asthma APGAR has been validated against the ACT in White children and adults but has not been validated against the ACT in African American or Hispanic Latino populations. We will use this opportunity to assess the validation to consider whether or not this brief control assessment could be used in African American/Black or Hispanic/Latino populations.

### 4. Total health care utilization and asthma-related healthcare utilization:

To assess the potential impact of use of PARTICS on the patient's health care utilization

will be evaluated during the follow up months of the study for all enrolled patients and comparing those in the enhanced usual care with those in the intervention group. We will also collect utilization data for the 12-month period before enrollment to assess changes in health care utilization within the enhanced usual care and within the intervention group for the period prior to enrollment and the annualized total health care utilization for the enrollment period.

Utilization will be based on review of the patient's insurance claims record for those sites with access to insurance data and health care system's billing data and EHR for all visits and procedures at any site (e.g. outpatient, urgent care, emergency department, hospital-based) for integrated delivery systems. For those clinics that are part of a system that includes pharmacy fulfillment data and/or insurance claims data, we will include all prescription medications that the patient obtained from the pharmacy.

Asthma-related health care utilization will be considered to include all visits and procedures which include asthma as a diagnosis in the outpatient and urgent care setting and for which asthma is a first or second diagnosis for emergency department or hospitalizations. While this is not likely to be completely accurate picture of the amount of time spent on asthma during particularly out-patient visits, it is a conservative estimate and unlikely to involve a systematic difference in billing procedures between the two study arms or before and during study enrollment.

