## **C. Participant Recruitment, Screening, Enrollment, and Follow-up**

### **1. Eligibility Criteria**

#### **INCLUSION CRITERIA**

- Black or Hispanic based on self-identification (Hispanic if identify as both)
- Male and female, ages 18-75 years
- Ability to provide informed consent
- Clinical history consistent with asthma for > 1 year.
- Prescribed ICS as daily maintenance therapy
- Participant must also have an ACT score of 19 or less, **or** a history of one or more exacerbations in the past year that required patient report of systemic corticosteroid use.

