All exacerbations will be reviewed by a team of 3 physicians blinded to the patient study assignment. A study nurse or coordinator will obtain the documents required for review and make sure that any information related to study arm assignment, intervention or enhanced usual care, is redacted. Drs. [name], [name] and [name] will do the initial review. If all 3 agree that it is or is not an exacerbation that decision will be accepted. If they do not have unanimous agreement, the event and all information will be sent to the adjudication team, Drs. [name], [name] and [name] to make a final decision. All physicians assessing or adjudicating exacerbations will be blinded to randomization.

The Policy Stakeholder Group requested additional data elements for secondary analyses-- total number of asthma related visits made to the enrolling site, ED visits, hospitalizations, and total asthma medication usage. The Policy Stakeholder Group was interested in how PARTICS might affect visits not associated with an exacerbation and thus not captured with our original data collection plan. In addition to asking patients on their monthly questionnaires, we will also ask all sites to provide site-generated billing data for their patients from one year prior to the date of consent 12 to 15 months following consent (depending on when the patient was enrolled). It will be adjusted for a 12 month rate. Thus, we will be able to compare between-groups visit frequencies as well as within-group visit frequencies over time. The impact on total asthma medication could influence the ease of acceptance of this strategy during dissemination.

Full study differences: The additional questionnaires used in the Vanguard (as noted above in pages 38-39) will not be included in the Full study monthly questionnaires.

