The analyses on the exploratory outcomes will also be performed. The rate on asthma deteriorations will be reported by treatment groups. The composite endpoint of asthma deteriorations or exacerbations will be analyzed using the same Andersen-Gill version of the Cox proportional hazards model as used in the primary analysis. The Asthma APGAR data will be analyzed using the same mixed model approach as described above in the Asthma Control Test (ACT) score analyses.

Data on the Asthma Medication Ratio (AMR) during the follow-up months, the total health care utilization (i.e., total number of visits made to the enrolling sites, total number of ED visits, and total number of hospitalizations), and asthma related health care utilization (i.e., number of visits made to the enrolling sites, number of ED visits, and number of hospitalizations for which asthma is a first or second diagnosis) will be summarized. Differences between two randomized treatment groups on these variables will be compared using either t-test or Kruskal-Wallis test if full follow-up is available on everyone or Poisson or Negative Binomial regression models with time as an offset to account for differential duration of follow-up.

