## **X. COVID-19 Sub study**

Background: The PREPARE study has produced riveting data/manuscripts regarding the COVID-19 pandemic and its impact on this disproportionately affected population of African American/Black and Hispanic/Latinx adults with asthma. First, a clinical communication published in May 2021 finding a 40% reduction in asthma exacerbations from January - August 2020 compared to January - August 2019 (during COVID-19) has had an overwhelming impact on researchers and the community. The finding was highlighted by several news agencies including the Atlantic. Additionally, a second manuscript has been accepted by JACI in Practice. Although we sampled only a subset of patients in the study, the findings showed that this population experienced changes in the quality of their asthma care and had increased socioeconomic stressors as a result of the COVID-19 pandemic and may be hesitant or unwilling to receive a COVID-19 vaccine.

The patient partners, stakeholders and research team agree that there is much more to be learned about this population with regards to COVID-19. In specific, we would like to better understand what might have contributed to the reduction in asthma exacerbations that we are measuring as our primary outcome. This involves understanding what practices have been undertaken by our population and, in order to make recommendations, to understand some of the attitudes toward COVID-19-induced modifications.

Aims: The aims of the sub study are to 1) explore subject behavioral changes which may have resulted in decreased exacerbations following the Covid19 pandemic. 2) explore patients' attitudes towards measures to prevent the spread of Covid19 (mask wearing, vaccine, etc.) and 3) investigate patient preferences towards telehealth vs. in person asthma clinic visits.

Methods: A COVID-19 questionnaire will be sent to PREPARE patients who agreed to be contacted after exiting the study. Approximately 1,000 agreed to future contact. The REDCAP, HIPPA compliant, questionnaire link will be sent via email and/or text and follow up of non responders will be by phone. As in the full study, to compensate patients for their time, we will pay patients \$25 for completing the questionnaire. Payment will be made through the BWH ADVARRA system.

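### Pre-enrollment utilization is collected in both arms but has no role in the between-arm comparison, and the within-arm changes it feeds are not labelled descriptive

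*Combined protocol and SAP*

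**What the plan says.** Utilization is an exploratory outcome. Section III.D.4 gives its purpose as "To assess the potential impact of use of PARTICS on the patient's health care utilization" and starts with the randomized contrast during follow-up, "comparing those in the enhanced usual care with those in the intervention group". It then adds: "We will also collect utilization data for the 12-month period before enrollment". The stated use of those earlier data is "to assess changes in health care utilization within the enhanced usual care and within the intervention group", with the enrollment period annualized. The only remark in that section on whether the two periods are comparable concerns billing practice.

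Section II.E.1 (Database Design and Administration) says the Policy Stakeholder Group asked for these data. It has every site supply billing data from one year before consent, puts rates on a 12-month basis, and expects to "compare between-groups visit frequencies as well as within-group visit frequencies over time".

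The analysis is in III.E.7: "Differences between two randomized treatment groups on these variables will be compared using either t-test or Kruskal-Wallis test". That applies if everyone has full follow-up. Otherwise a Poisson or negative binomial model with a time offset is used. No covariate, pre-enrollment count or within-arm test is named.

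Elsewhere the plan does use baseline information. The primary model (III.E.4) adjusts for past-year exacerbation, and the secondary mixed models (III.E.5) analyse change from baseline with the primary model's covariates.

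**The concern.** Two gaps follow from this.

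**Precision.** A full year of the same measure is gathered for both arms and then given no role in the only comparison that randomization protects. The protocol itself treats past exacerbations as a predictor of later ones (II.C.1, text after the eligibility lists), so the information is prognostic by its own account.

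**Interpretation.** Before/after change in each arm is planned in a section whose aim is the impact of PARTICS, without a statement that the figures are descriptive. By contrast, the next item (III.D.5, Medication Data) says outright that no formal tests are planned. The documents give three reasons other than PARTICS why utilization could change in both arms:

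- One entry route is "a history of one or more exacerbations in the past year" (II.C.1). For those patients the qualifying event lies inside the before window.
- Both arms receive care from Asthma IQ-trained providers, and VII.C.2 says this training improves asthma control.
- Section X reports a published result from this study "finding a 40% reduction in asthma exacerbations from January - August 2020 compared to January - August 2019". Figure 3 has enrollment from October 2017 to April 2020 and follow-up to May 2021, so this period falls mainly in after windows.

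At stake is how readers, including the policy group, interpret an exploratory result, and how tight its interval is.

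**Working it through.** **The plan's own figure.** No power or effect size is stated for utilization. The only input borrowed here is the control rate of 0.4 per year (III.E.8), so I checked that the power built on it reproduces.

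- Mean follow-up = 1.25 × (1 − 0.3125/2) = 1.055 years.
- Expected events = 600 × 1.055 × 0.4 = 253.1 (control) and 253.1 × 0.765 = 193.6 (PARTICS).
- SE of the log rate ratio = √(1/253.1 + 1/193.6) = 0.0955.
- Power = Φ(|ln 0.765|/0.0955 − 1.96) = Φ(0.85) = 0.80, as stated.

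**Precision lost between arms.** I used null trials with 600 patients per arm, gamma-Poisson counts, no treatment effect and 400 replicates. A share *q* of patients is enrolled because of at least one prior-year event, and the rest are unselected on prior events. The underlying means (0.16 to 0.33 per year) were chosen so that the enrolled cohort runs near 0.4. Neither *q* nor the dispersion is in the documents. The adjusted analysis was least squares with the prior count as a linear term, so it approximates the count model proposed below.

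| Dispersion | *q* | Variance ratio, adjusted/unadjusted | Reduction | Unadjusted between-arm test rejects |
|---|---|---|---|---|
| 1 | 25% | 0.927 | 7% | 4.75% |
| 1 | 50% | 0.945 | 5.5% | 3% |
| 2 | 50% | 0.89 | 11% | 4% |
| 2 | 75% | 0.934 | 7% | 4.75% |
| 4 | 50% | 0.82 | 18% | 4.5% |

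The unadjusted test keeps its level, so the loss is in precision only. Since √0.945 = 0.97 and √0.82 = 0.91, the interval would be about 3% to 9% narrower with adjustment.

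For frequent visits a closed form gives a rough idea. In an unselected gamma-Poisson cohort with stable frailty, the year-to-year correlation is r = θμ/(1 + θμ) and the variance reduction is r².

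- μ = 0.4, θ = 1: r = 0.4/1.4 = 0.29, so r² = 0.08.
- μ = 4, θ = 0.5: r = 2/3, so r² = 0.44.

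The values μ = 4 and both θ are assumptions.

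**Within-arm change with no treatment effect.** With the same model, I fixed the follow-up rate at 0.4 and let dispersion run from 0.5 to 4. Worked case (dispersion 1, *q* = 50%, underlying mean 0.288):

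- P(at least 1 prior event) = 1 − 1/1.288 = 0.224.
- Prior mean among those selected = 0.288/0.224 = 1.29.
- Cohort prior mean = 0.5 × 1.29 + 0.5 × 0.288 = 0.788.
- Change = 0.4/0.788 − 1 = −49%.

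| *q* | Change | Change if the last pre-enrollment month is event-free |
|---|---|---|
| 0% | 0% | +9% |
| 25% | −30% to −33% | −26% to −29% |
| 50% | −48% to −50% | −46% to −48% |
| 75% | −60% | −59% |
| 100% | −67% | −67% |

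The last column reflects the exclusion for acute asthma care in the past month (II.C.1). In the null trials above (*q* from 25% to 75%), a paired within-arm test rejected in every replicate. The plan specifies no such test; this only shows what one would do.

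**The case against.** The case against is substantial, and most of it stands.

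- **A reader might infer that within-arm falls are offered as proof that PARTICS works.** The text does not say so. III.D.4 puts the randomized comparison first, the before/after look covers both arms alike, and III.E.7 specifies no within-arm test or causal claim. What remains is the missing descriptive label.
- **A reader might infer that the cohort was selected for a bad year, so each arm must show a fall.** Entry needs an ACT score of 19 or less *or* a prior-year exacerbation. ACT alone suffices, the share entering by each route is not stated, and the past-month exclusion pulls the other way. The table runs from +9% to −67% depending on that share. Total visits are also less tied to the entry rule than exacerbations are.
- **A reader might infer that the between-arm test is biased or bars baseline data.** It is neither: randomization protects it, and the plan is silent on covariates. With 12 to 15 months of follow-up (II.C.7) and 25% annual loss assumed, the regression branch probably applies, and it could take them.
- **A reader might object to unequal before and after windows.** Both II.E.1 and III.D.4 annualize, so this is not a defect.
- **A reader might take 44% as the expected gain.** It rests on an assumed visit rate, an assumed dispersion and frailty that does not change between years.

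The study team is also already examining the pandemic fall (Section X), so it is unlikely to credit that fall to PARTICS.

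**Conclusion.** The point holds as a modest improvement to an exploratory outcome. The between-arm comparison of utilization is valid but leaves collected information unused. The gain from using it is about 5% to 18% of the variance for exacerbation-like events, and possibly more for frequent visits, all under assumed dispersion and entry mix. The within-arm changes cannot be attributed to PARTICS, because of partial selection on prior events, Asthma IQ in both arms and the pandemic. How far regression to the mean would move them is unknown. No primary or secondary inference, sample size or type I error is affected. Severity is low.

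**What to change.** In III.E.7, compare the arms on each utilization count by negative binomial regression. Keep the follow-up-time offset and add the patient's own 12-month pre-enrollment count of the same item, for example as log(count + 1). Report the between-arm rate ratio with its interval. The Asthma Medication Ratio is not a count and is outside this change.

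In III.D.4 and II.E.1, state that within-arm before/after changes are descriptive only and that inference about PARTICS rests on the between-arm rate ratio.

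The cost is wording alone, since II.E.1 already asks all sites for the pre-enrollment data. Where those data are missing, the multiple imputation already planned in III.E.10 can be used, with utilization added to its pre-specified variables.

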##### 5. Medication Data:

For patients randomized to the intervention group, the amount of QVAR use (estimated in total refills per period) due to PARTICS treatment will be reported by summary tables. Information on all other medication use will be available only in subset of patients for whom pharmacy fulfillment data is available from their health system. When available, the total number of dispensed inhalers for all of the patients' usual maintenance medications and usual rescue medications will be reported in summary tables.

No formal statistical tests are planned.

#### **E. Biostatistical Analysis, Statistical Design, and Sample Size**

##### Vanguard data validation

The data transfer process will be tested in the Vanguard study. Data collected from Vanguard process will be transferred from the Patients Engaged Electronic Reporting System (PEERS) developed by the University of Colorado, Department of Family Medicine (CUDFM) to DCRI. The verification of data transfer integrity will be performed at DCRI according to DCRI SOP.

Unexpected data inconsistencies within and between data sources will also be examined and reported. It will help to determine if additional data queries or validation rules will need to be developed to ensure the data quality in the full study.

Randomization data from PEERS system will be compared with the original randomization scheme generated by DCRI to make sure the PEERS system randomization data match the randomization scheme created by DCRI. The randomization slots actually used by Vanguard patients will also be examined to make sure the randomization process works as

planned in the Vanguard study.

Data collected through Vanguard process will be summarized by randomized treatment using appropriate descriptive statistics. Descriptive summaries of the continuous variables will be presented in terms of mean, standard deviation and percentiles (e.g., median, 25th and 75th percentiles), while discrete variables will be summarized in terms of frequencies and percentages. Due to the small sample size of the Vanguard study, no formal statistical tests will be performed.

Data report will focus on the Vanguard specific questions that survey about the study enrollment process, intervention process, monthly questionnaire process, and medication refill process. In addition, the screen failure data, patients' adherence barrier data from ASK-12, reasons of patients' drop-out or premature discontinuation, data on missed visits will also be carefully examined and reported. These data will help the study team to identify the barriers of patient enrollment, treatment compliance, and patient and physician adherence.

**Full study differences:** Formal statistical analyses will be performed.

## 1. Overview

Statistical analysis will be performed at the Statistical Data Coordinating Center at Duke Clinical Research Institute (DCRI). The study will use a randomized, parallel design to test the addition of PARTICS to provider-educated care as compared to continuation of provider-educated care. All major treatment comparisons between the randomized groups in this trial will be performed according to the principle of "intention- to-treat" (ITT); that is, subjects will be analyzed according to the treatment arm they were randomized to regardless of their compliance with the study medication.

Data collected in this study will be documented using summary tables with appropriate descriptive statistics for continuous variables and binary variables.

Annualized rates of count outcomes will be summarized using the annualized mean occurrence based on the Poisson model. In addition, survival curves will be constructed for all time to event endpoints using Kaplan-Meier methods.

Unless otherwise specified, the statistical analyses procedures for comparisons of the two groups will be as follows: 1) Two-sample t test or Kruskal-Wallis test for continuous parameters; 2) Chi-square test of independence for binary comparisons unless the number of events is less than 10, in which case Fisher's exact test will be used; 3) Cochran Mantel-Haenszel Modified Ridit Scores for non-time-to-event categorical variables with >2 categories (nominal variables will be compared using the General Association p-value; ordinal variables will be compared using the Row Mean Score p- value); 4) Andersen-Gill adaptation of Cox regression for time-to-event variables with more than one occurrence. 5) Log- rank test for first occurrence of time-to-event variables. All statistical tests and/or confidence intervals, as appropriate, will be performed at  $\alpha=0.05$  (2-sided) unless specified otherwise. SAS statistical software (version 9.1 or higher) will be used in analyses, unless otherwise noted.

## 2. Background Data and Baseline Characteristics:

Baseline demographic and clinical characteristics, including age, gender, socioeconomic status (SES), ethnic groups (Hispanic/Latino or African American), smoking status, BMI, medical

history/comorbidities, asthma history, and asthma medication use (e.g., ICS/LABA use vs. ICS use) will be summarized for each randomized treatment arm of the study. Asthma exacerbations during the 12 months prior to randomization will also be reported.

In addition, data on patients' attitude towards ICS (by the Beliefs about Medications Questionnaire - BMQ), healthy literacy level (by S-TOFHLA questionnaire), depression level (by Patient Health Questionnaire—PHQ-2), treatment adherence likelihood (by ASK-12 questionnaire) will also be tabulated by randomized treatment groups.

Asthma exacerbations, Asthma Control Test (ACT) scores, lost days of work or schools within one month prior to randomization will also be reported using summary tables.

Only descriptive statistics will be reported for the baseline data. Continuous variables will be presented in terms of mean, standard deviation, and percentiles (e.g., median, 25th and 75th percentiles), while discrete variables will be summarized in terms of frequencies and percentages.

### **3. Treatment Compliance**

Treatment Compliance will be monitored throughout the study. Numbers of patients non-compliant with treatment or crossing-over will be documented using counts and rates over time.

Sensitivity analyses will be performed for patients who have treatment cross- overs.

The primary analysis will be based on an Intention-to-treat analysis, but we will also conduct a Per Protocol analysis with available data.

### **4. Statistical Analysis for Primary Outcome**

The primary aim of the study is to determine the impact of PARTICS on asthma outcomes in a minority population consisting of African American and Hispanic/Latino adults. The primary outcome of this study will be the intensity of asthma exacerbations during the months of follow-up between those patients randomized to addition of PARTICS to provider-educated care vs. those who continue with provider-educated care alone.

Rate of asthma exacerbations per year will be reported for two treatment groups. Annualized rates of count outcomes will be summarized using the annualized mean occurrence based on the Poisson model.

Exacerbations rates during follow-up will be compared using the Andersen-Gill adaptation of time-to-event Cox proportional hazards model with robust standard errors to account for potential multiple occurrences of the outcome in each patient (Andersen Gill, 1982). This model was selected over the more commonly used time to first event Cox model for two reasons. First, we believe that total experience during follow-up matters more to patients than the onset of the first exacerbation. Second, the power is increased when multiple events can be included. The covariates in the primary comparison will include: study center (to account for any geographic variation in patterns of care), h/o exacerbations in the past year (y/n), on ICS/LABA prior to randomization (Y/N), race/ethnicity, smoking status (as defined for subgroups), age, BMI (body mass index), and gender since all may influence the rate of exacerbations or the response to corticosteroids. The primary effect will be based on the randomized treatment arm indicator

variable.

Time from randomization to first asthma exacerbation will be compared using the log-rank test. In addition, survival curves will be constructed for this time-to-event endpoint using Kaplan-Meier method.

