## 2. Full Study

Tool or domain	Baseline	Monthly	Final Survey
Eligibility	X		
Demographics	X		
Co-morbidities	X		
Asthma medications	X	X	X
Exacerbations	X	X	X
Smoking status	X	X	X
Lost days of work or school	X	X	X
Beliefs about Medications Questionnaire—asthma	X		
Health Literacy-Brief Form	X		
PHQ-2	X		
MARS-5 adherence questions	X		X
Perceived Stress Index	X		
Asthma Symptom Utility Index	X	X	X
Asthma APGAR (control)	X	X	X
Asthma Control Test	X	X	X
Payers Scale	X		
Everyday Discrimination Scale (SHORT)	X		
Satisfaction with therapy (intervention only)			X
Refill information		X	X
Address change		X	
Permission to contact for additional questions related to PREPARE			X
Permission to contact for future studies			X
COVID-19 questionnaire (SHORT)		X	X

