## **2. Data Monitoring and Site Auditing**

The PEERS system will be programmed such that patient intake, baseline and monthly questionnaire data is required to be completed prior to advancing to the next section. Thus, patients who complete the consent, enrollment, baseline and monthly data collection processes should have complete data. All outcome data will be selected from radio button or pick list questions and thus data will be codified at the time of capture. The PEERS system will also provide an administrative section for each site as well as the local research team. This section will provide patient contact information following consent. Allow messaging between the sites and the AAFP NRN staff and allow study staff to collect patient data using a computer assisted survey process when needed. Sites are primarily being asked to enroll patients. The eligibility criteria will be built into the consent process. The enrollment rate will be tracked using the administrative processes for the AAFP NRN within PEERS. If a site uses a paper method for any consents then an administrative page will be created to allow the local site to complete the eligibility criteria after consent is obtained. These sites will be monitored by a daily PEERS report to the central AAFP NRN staff. If a site appears to be struggling with recruitment the AAFP NRN staff may make a site visit to see if they can assist with rethinking the recruitment

process.

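### The primary Andersen-Gill model leaves out baseline ACT, a risk marker already collected on every patient, and so probably gives up some precision

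*Combined protocol and SAP*

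**What the plan says.** Section III.E.4 compares exacerbation rates with the "Andersen-Gill adaptation of time-to-event Cox proportional hazards model with robust standard errors". The covariate list opens with "The covariates in the primary comparison will include: study center", continues with "h/o exacerbations in the past year (y/n), on ICS/LABA prior to randomization (Y/N), race/ethnicity, smoking status (as defined for subgroups), age", and closes with "BMI (body mass index), and gender since all may influence the rate of exacerbations or the response to corticosteroids". That makes eight covariates, and baseline ACT is not one of them.

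ACT appears elsewhere in three roles:

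- **Entry.** The last inclusion criterion in II.C.1 reads "Participant must also have an ACT score of 19 or less", with one or more exacerbations in the past year as the alternative.
- **Data.** The full-study schedule in II.D.2(b) has "Asthma Control Test" at baseline, monthly and at the final survey. II.E.2 says that "baseline and monthly questionnaire data is required to be completed prior to advancing to the next section".
- **Risk marker.** The study overview in II.A describes patients at risk of exacerbation by three examples: poor control on a controller ICS, an exacerbation in the previous 12 months, and use of ICS/LABA.

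The primary list is reused in the secondary mixed models (III.E.5), the subgroup models (III.E.6) and the composite of deteriorations or exacerbations (III.E.7).

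**The concern.** The plan chooses covariates because they may influence the exacerbation rate or the response to corticosteroids. By that test baseline ACT looks like a candidate. Of the three risk markers in II.A, two are in the model and the third, poor control, is left out without a reason.

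The entry rule adds to this. Because it is ACT of 19 or less or a past-year exacerbation, every patient without such a history has a low ACT. ACT and history are therefore linked by selection, which favors adjusting for both rather than for history alone.

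What is at stake is precision. If ACT explains part of the between-patient variation in exacerbation rates beyond the listed covariates, the robust standard error of the treatment effect is wider than the collected data require. The same holds in the Andersen-Gill models that reuse the list.

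**Working it through.** **1. Reproduce the plan's power (III.E.8).** The inputs are 600 per arm, a control rate of 0.4 per year, a 23.5% reduction (ratio 0.765), 15 months of follow-up, 31.25% uniform loss and two-sided 0.05.

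- Mean follow-up: T = 1.25 × (1 − 0.3125/2) = 1.055 years.
- Expected events: 600 × 0.4 × 1.055 = 253.1 in control and 253.1 × 0.765 = 193.6 in PARTICS, or 446.8 in all.
- SE of the log ratio: √(1/253.1 + 1/193.6) = 0.0955.
- Power: |ln 0.765|/0.0955 = 0.268/0.0955 = 2.81, and 2.81 − 1.96 = 0.85, which gives 80.1%.

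The stated 80% is reproduced with no covariate adjustment at all. Under this homogeneous Poisson rate, adding ACT would gain nothing.

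**2. Simulate the primary model with and without ACT.** The documents give no ACT-to-exacerbation association and no between-patient variance, so both are assumed.

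- ACT before selection: mean 17 (assumed), SD 4.9. The SD is the III.E.8 figure for ACT as an outcome.
- Past-year exacerbation: 50% before selection and a rate ratio of 2 (both assumed).
- Entry: ACT of 19 or less, or history. The selected pool then has mean ACT 15.9, SD 4.3, history in 59%, and an ACT-history correlation of 0.27.
- Residual gamma frailty variance: 0 or 1 (assumed).
- Rates, loss, sample size and ratio: as in step 1.

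Each setting has 600 trials, fitted by Andersen-Gill with robust SE. History is in both models.

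| Rate ratio per 4.9 points worse ACT | Frailty variance | SE without ACT | SE with ACT | Variance ratio | Power without → with |
|---|---|---|---|---|---|
| 1.0 | 0 | 0.0955 | 0.0955 | 1.000 | 79.8% → 80.0% |
| 1.0 | 1 | 0.1149 | 0.1149 | 1.001 | 62.2% → 62.2% |
| 1.2 | 0 | 0.0963 | 0.0957 | 0.988 | 82.2% → 83.8% |
| 1.2 | 1 | 0.1152 | 0.1147 | 0.991 | 65.7% → 66.5% |
| 1.5 | 0 | 0.0983 | 0.0953 | 0.939 | 79.8% → 81.3% |
| 1.5 | 1 | 0.1191 | 0.1165 | 0.958 | 60.8% → 63.0% |
| 2.0 | 0 | 0.1052 | 0.0958 | 0.830 | 72.8% → 79.2% |
| 2.0 | 1 | 0.1291 | 0.1214 | 0.884 | 54.7% → 61.3% |

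Monte Carlo error on each power is about 2 points. The mean log hazard ratio with and without ACT differs by at most 0.0023 in any row (−0.2698 against −0.2675), so leaving ACT out does not visibly shift the estimate.

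**3. Cross-check in closed form.** With total between-patient variance k, Var = 0.0955² + 2k/600. Adjusting for a covariate with log rate ratio b per SD divides (1 + k) by exp(b²). Take k = 0.5 and a rate ratio of 1.5:

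- b² = 0.164, so the residual is 1.5/1.179 − 1 = 0.273.
- SE falls from 0.1038 to 0.1001, a variance ratio of 0.930.
- That is worth 1200 × (1/0.930 − 1), or about 91 patients.

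Over k from 0.25 to 2, a rate ratio of 1.2 is worth 17 to 25 patients and 1.5 is worth 81 to 128. This form ignores the narrower ACT spread after selection and the overlap with history. Its gains at 1.2 and 1.5 therefore run higher than the simulated ones, and I rely on the simulation.

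**The case against.** The strongest reply is that there is no error here. Eight covariates are pre-specified with a reason. Leaving out a ninth causes no bias, does not inflate type I error and contradicts no section. The power statement takes no credit for covariates. All of that stands.

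Three further points stand:

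- The gain rests on an association that the documents never quantify. Section II.C.1 expects exacerbations in one third of patients who are poorly controlled on ICS or who use ICS/LABA. That is a rate for the combined group, not a gradient in ACT.
- The simulation adjusted for history only. The actual model also has center, ICS/LABA, race/ethnicity, smoking, age, BMI and gender, so any overlap of ACT with these lowers the gain.
- In a Cox-type model an added covariate is not certain to shrink the standard error. The gain comes through the robust variance, when ACT explains heterogeneity between patients.

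A reader might also infer that history should enter as a count. The documents do not support that. Section II.E.1 defines the covariate as prior corticosteroid bursts, yes or no, and warns about recall. The baseline section says "Asthma exacerbations during the 12 months prior to randomization will also be reported", which does not show that a number is recorded. Nor does it matter that omitting ACT may attenuate the history coefficient, since no stated aim estimates it.

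None of this supplies a reason to leave ACT out. It limits how much can be claimed for putting it in.

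**Conclusion.** The point holds as a low-cost efficiency improvement. Baseline ACT is absent from the primary model although it is collected on every patient, is used for entry, and reflects a risk marker that the plan itself names. Adding it would lower the robust variance of the log hazard ratio by about 0%, 1%, 4-6% or 12-17% at assumed rate ratios of 1.0, 1.2, 1.5 or 2.0 per 4.9 points. In power this is about 0, 1-2, 2 and 6-7 points. These figures are on the generous side, because only history was in the comparison model.

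Two stronger readings do not follow. One is that the primary comparison is biased or invalid. Randomization protects it, and the estimates with and without ACT agree. The other is that the 80% power claim fails for want of ACT. It reproduces at 80.1% with no covariates. The lower powers in the table come from the assumed variation between patients, of which ACT recovers only a part.

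**What to change.** Add baseline ACT, as a continuous score, to the covariate list in III.E.4, and keep exacerbation history as yes/no. State that the change carries into III.E.5, III.E.6 and III.E.7, which reuse the list. In III.E.5 this also gives the model for change in ACT its own baseline value as a covariate, which is not listed there now.

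Make the change by a dated, justified amendment before anyone outside the unblinded statistical team sees results by arm. This version is late: Figure 3 ends follow-up on May 1, 2021, and section X already refers to patients who have exited. If unblinding has passed, leave the primary model as it is and report the ACT-adjusted model as a labelled sensitivity analysis.

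The cost is one model term and the amendment. No new data are needed.
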